Study Rationale	
Heart failure (HF) is prevalent in more than 6 million Americans and is a leading cause of hospitalizations. Active HF self-management reduces hospitalizations but patient adherence to HF self-care behaviors is poor. Data suggests that family involvement in the patient's care enhances patients' self-management.
 
Patient and family engagement is critical to obtaining the knowledge, skills, and confidence for effective self-management. Engagement is often manifested through asking questions, expressing concerns, and clarifying information from health care providers (HCPs). Engagement is generally low among individuals with HF.
 
Strategies such as pre-visit prompt lists can enhance patient and family engagement by encouraging patients and family members to ask relevant questions and discuss sensitive topics with HCPs. However, several important gaps in the literature exist. First, the effect of prompt lists on self-management has not been tested. Second, few studies have used them with family members. Lastly, prompt lists have not been tested in HF patients.

Study Objective(s)	The specific aims of this pilot study are to: 1) Develop a pre-visit question prompt list for use with HF patients and family members; and 2) Conduct a pre-post pilot study in up to 30 HF patients and family members to evaluate feasibility, acceptability, and effects of the prompt list on HF self-care behaviors (of patients and family members/caregivers), communication behaviors, and self-efficacy with communication.
Test Article(s) (If Applicable)	The question/topic prompt list is the main intervention in this study. A prompt list is a written document containing suggested questions that the family member and/or patient may want to ask the health care provider during the visit. A section is included for the patient to check which behaviors they would like for their family member to engage in during the visit and space is provided for the family member to check which behaviors they are willing to perform during the visit.
Study Design	Single group pre-post design
Subject Population	We will enroll adult patients with HF, family members, and HCPs. Patient Eligibility Ambulatory adult patients ≥ 30 years old

key criteria for Inclusion and Exclusion:	
Receive care in the UNC Cardiology or General Internal Medicine practice
 
Have a clinical diagnosis of HF
 
Currently prescribe a loop diuretic
 
Have a New York Heart Association class II-IV
 
Must speak English
 
Must have a working telephone or live with the patient

	
Family Member Eligibility
 
Must be at least 18 years old and able to give informed consent
 
Must be willing to participate in the intervention activities and provide informed consent
 
Must speak English
 
Must have a working telephone or live with the patient

	
Health Care Provider Eligibility
 
Must be an MD or advance practice provider (NP or PA) in the UNC cardiology or General Internal Medicine practice
 
Must be willing to have an enrolled patient visit audio-taped

Number Of Subjects	Up to 80 participants, including up to 30 HF patients and family members, and HCPs
Study Duration	
Each subject’s participation will last up to 6 months
 
The entire study is expected to last 1 year

Study Phases Screening Study Treatment Follow-Up	
(1) Screening: screening for eligibility and obtaining consent and (2) Intervention: study intervention; and (3) 2-day post clinic visit and 1 month follow-up

Efficacy Evaluations	
Primary outcome: Percent of eligible patients and companions who enrolled in the study.
 
Secondary outcomes: 1) mean acceptability checklist score, 2) mean score on self-care of heart failure index scores (maintenance, management, and confidence subscales); 3) mean score on caregiver contribution to self-care of heart failure index scores (maintenance, management, and confidence subscales); 4) mean score on perceived efficacy in patient-physician interactions score; 5) mean score on communication with physicians measure

Pharmacokinetic Evaluations	N/A
Safety Evaluations	N/A
Statistical And Analytic Plan	This is a pilot study and as such, our sample size was selected based largely on feasibility. Specifically, we examined the expected margin of error for varying recruitment and recruitment yields.
DATA AND SAFETY MONITORING PLAN	We will not have a DSMC, DsMC, or DMC for this study given that the safety risk to participants is extremely low.

1 BACKGROUND AND RATIONALE

Heart failure (HF) is prevalent in more than 6 million Americans and is a leading cause of hospitalizations. Active HF self-management reduces hospitalizations but patient adherence to HF self-care behaviors is poor. Data suggests that family involvement in the patient's care enhances patients' self-management.

Patient and family engagement is critical to obtaining the knowledge, skills, and confidence for effective self-management. Engagement is often manifested through asking questions, expressing concerns, and clarifying information from health care providers (HCPs). Engagement is generally low among individuals with HF.

Strategies such as pre-visit prompt lists can enhance patient and family engagement by encouraging patients and family members to ask relevant questions and discuss sensitive topics with HCPs. A prompt list is a structured list of questions or topics related to illness, treatment, and support that is developed from interviews with patients, family members, and HCPs. Prompt lists are completed by patients and family members before a visit. Prompt lists have been shown to increase the number and relevance of questions asked by patients and family members. However, several important gaps in the literature exist. First, the effect of prompt lists on self-management has not been tested. Second, few studies have used them with family members. This gap is important given that about 1 in 3 adults are accompanied to medical visits by a family member. Moreover, family members' concerns are often ignored by HCPs, thus adversely affecting families' ability to support patients' self-management. Lastly, prompt lists have not been tested in HF patients. Most of the research on their use has been conducted in cancer patients facing oncology-specific clinical decisions. To address these gaps, we will:

1) Develop a pre-visit question prompt list for use with HF patients and family members; and 2) Conduct a pre-post pilot study in up to 30 HF patients and family members to evaluate feasibility, acceptability, and effects of the prompt list on HF self-care behaviors (of patients and family members/caregivers), communication behaviors, and self-efficacy with communication.

This study will take place in the UNC Cardiology clinic or the General Internal Medicine clinic at the Ambulatory Care Center.

1.1 Name and Description of Investigational Product or Intervention

A question/topic prompt list is the main intervention in this study. A prompt list is a structured list of questions or topics related to illness, treatment, and support that the family member and/or patient may want to ask the HCP during the visit. The prompt list includes a section for the patient to check which behaviors they would like for their family member to engage in during the visit and space is provided for the family member to check which behaviors they are willing to perform during the visit.

1.2 Non-Clinical and Clinical Study Findings N/A

1.3 Relevant Literature and Data. See section

2 STUDY OBJECTIVE

The objective of the study is to evaluate feasibility, acceptability, and effects of the prompt list on HF self-care behaviors (of patients and family members/caregivers), communication behaviors, and self-efficacy with communication in up to 30 HF patients and family members.

3 INVESTIGATIONAL PLAN (Brief Overview)

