3.1 Study Design

This is a single-group pre-post prospective study design.

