3.2 Allocation to Treatment Groups and Blinding (if applicable) N/A

3.3 Study Duration, Enrollment and Number of Subjects. After IRB approval, the study will be active until 1-month follow-up data has been collected on all study participants (i.e., up to 30 dyads.) We anticipate that be no longer than 1 year.

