4 STUDY PROCEDURES

4. 1 Screening/Baseline Visit procedures: Thirty HF dyads will receive the prompt list. Each dyad member will receive a prompt list to complete in the clinic waiting room immediately before their appointment. HF dyads will complete the prompt list without staff help. Completing the prompt list involves two steps. In step 1, participants will independently select from a list of questions or write in their own questions they would like to ask their health care provider during the visit. Patients will also be asked to select among a pre-determined list of behaviors they would like their family member to engage in during the visit (e.g., write down the providers instructions). In step 2, dyad members will collaboratively decide which questions to discuss during the visit. Participants will be encouraged to take the prompt list into the exam room and use it to facilitate communication with the HCP. The RA may take a picture of the prompt lists (which will not contain any identifying information, only a study id) to assess areas of agreement and disagreement between the dyad on what to discuss with the HCP. This information will inform future studies.

Potential participants will be identified using several sources: the Carolina Data Warehouse (CDW-H); the HF social support and family studies registry (SSR; IRB #11-0562); medical record audits by the study PI; and suggestions from HCPs.

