
Partners in Health Eligibility SCREENING FORM

The following form will be used to determine eligibility for Patients:

Partners in Health: Pilot test of a Pre-Visit Question Prompt List to Enhance Engagement of heart failure (HF) patients and Family Members During Medical Visits

Patient Eligibility Form

Research Assistant: _____

Study ID#: _____

QUESTIONS TO ASK PATIENT TO VERIFY ELIGIBILITY

DATE: _____

1. Is English your preferred language?"
YES NO
2. "Do you see a health care provider at the UNC Cardiology Clinic?"
YES NO
3. "Do you have a diagnosis of Heart Failure (or Diastolic Dysfunction)?"
YES NO
4. "Do you take a loop diuretic medication?" (e.g. Furosemide, Lasix, Bumetanide, Bumex, Demadex, Torsemide)
YES NO
5. "Do you take a thiazide diuretic medication?" (e.g. Hydrochlorothiazide, HydroDIURIL, Chlorothiazide, Diuril, Chlorthalidone, Metolazone, Zaroxolyn, Indapamide, Lozol)
YES NO
6. "What is your current age?"
7. "Do you require assistance with basic activities of daily living?"
YES NO
8. "Do you live in a nursing home or care facility?"
YES NO

(Patients who receive nursing home services (including help with basic activities of daily living are NOT eligible to participate; patients living independently in senior centers or independent living facilities ARE eligible)

9. Do you have a working telephone?
YES NO
10. Do you agree to have one of your visits with your provider audiotaped
YES NO
11. Symptom Assessment (Patient must answer "YES" to at least one question)

"Think about the last six months and the days you felt the worst.

So, on your worst days..."

1) "How many city blocks could you walk before getting short of breath?"

If states a specific number, has symptoms (Number _____ = symptoms)

YES

If says can walk as far as s/he wants—go to #2

NO

If unable to walk enough to answer question, go to 1a below

Unable to answer

2) "Did you have to walk at a slower pace than normal to keep from getting short of breath?"

If says Yes, has symptoms

YES

If says No—go to #3

NO

3) "If you had to rush or hurry, did you get short of breath?"		
If says Yes, has symptoms		YES
If says No—go to #4		NO
4) "How many flights of stairs could you climb without getting short of breath or needing to stop to catch your breath?"		
If less than 2 flights or needs to stop at 2 flights catch breath, has symptoms		YES
If can walk up 2 or more flights then is truly class I and does not have symptoms		NO

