6.3 Statistical Methods

Analysis for this study will be quantitative pre-post analyses. We will compute descriptive statistics (percentages, means, and standard deviations) for feasibility, acceptability, and behavioral outcomes. For each behavioral outcome (HF self-care behaviors, self-efficacy related to self-care, communication with provider, communication with providers, and perceived efficacy in interactions with doctor), we will use paired t-tests to compare changes in mean scores from baseline to 1-month separately for accompanied patients, companions, and unaccompanied patients. In this pilot study, we are not conducting hypothesis testing. To help plan for future proposals, point estimates of effect sizes for the mean change value in each behavioral outcome will be computed as the ratio of the mean difference in each change value between baseline and 1-month follow-up.

6.4 Sample Size and Power.

This is a pilot study and as such, our sample size was selected based largely on feasibility. Specifically, we examined the expected margin of error for varying recruitment and recruitment yields.

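### A single-group pre-post change cannot show the effects of the prompt list, and the planning effect sizes in Section 6.3 could mis-size a future trial in either direction

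*Combined protocol and SAP*

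**What the plan says.** Section 2 gives the aim: "The objective of the study is to evaluate feasibility, acceptability, and effects of the prompt list on HF self-care behaviors", and extends it to communication behaviors and self-efficacy. The Synopsis and Section 1 word the aim the same way. Section 1 also lists the untested effect of prompt lists on self-management as a gap in the literature and presents this pilot as a response to it.

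Section 3.1 states the design: "This is a single-group pre-post prospective study design". Section 4.1 leaves nobody without the intervention: "Thirty HF dyads will receive the prompt list". Section 3.3 keeps the study open until "1-month follow-up data has been collected on all study participants (i.e., up to 30 dyads".

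Section 6.3 compares baseline with 1 month by paired t-tests and adds: "To help plan for future proposals, point estimates of effect sizes for the mean change value in each behavioral outcome will be computed". It calls the effect size a ratio but names only the numerator. It mentions no confidence interval and does not say what the change may be attributed to. It also says that no hypotheses are being tested.

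On sample size, Section 6.4 says "our sample size was selected based largely on feasibility" and that "we examined the expected margin of error for varying recruitment and recruitment yields". It gives no alpha, power, SD, effect size or margin.

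**The concern.** The word effects in the objective is a causal claim about the list. The data will contain one number per outcome, the change across an appointment, and that change has several possible sources besides the list: the provider's own advice at the visit, a recording that the provider has been reminded of, and the study's interviews. A list with no effect could still be followed by a change in the scores.

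Two things are at stake. First, Section 12 plans a paper on the primary and secondary outcomes, so the attribution could reach print. Second, Section 6.3 intends the change to inform later proposals. A controlled trial is sized on the difference between arms, and a within-group change estimates that difference only if the comparison arm would not change at all.

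**Working it through.** **Can the design identify the list's effect?**

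- Comparator: none, concurrent or historical (Sections 3.1 and 4.1).
- Unaccompanied patients, named in Section 6.3, are not a control. Section 4.1 requires both dyad members to enroll, and no group without the list is described.
- Between the two measurements: the appointment itself, its audio-recording (Section 4.1, intervention procedures) and the 2-day call, which covers communication and perceived efficacy (Section 4.2). The 1-month assessment is timed from the appointment (Section 10).

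So observed change = list effect + non-list change, and only the sum is observed.

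**The plan's own figure.** Up to 30 dyads cannot be reproduced, because Section 6.4 gives no inputs.

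**What follows if the sum is used as a between-arm effect.** All inputs here are assumptions: two-sided alpha 0.05, power 80%, two equal arms, SD 1, pilot d = 0.5. Let s be the share of the pilot change that is not due to the list, so true d = 0.5 × (1 − s). Approximately, n per arm = 2 × (1.960 + 0.842)² / d². For d = 0.5 this is 15.70 / 0.25 = 62.8, or 63; the two-sample t-test gives 64. The table uses the t-test.

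| s | True d | n per arm needed | Power at 64 per arm |
|---|---|---|---|
| −25% | 0.5 × 1.25 = 0.625 | 42 | 94% |
| 0 | 0.5 | 64 | 80% |
| 40% | 0.5 × 0.6 = 0.3 | 176 | 39% |
| 50% | 0.5 × 0.5 = 0.25 | 253 | 29% |

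The required size scales by about 1/(1 − s)²: 2.8 times at 40%, 4 times at 50%, and 0.64 times at −25%.

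**Missing denominator.** With equal SDs at the two times and pre-post correlation r, dividing by the SD of change instead of the baseline SD multiplies the effect size by 1/√(2(1 − r)). For assumed r of 0.3, 0.5 and 0.7 the factor is 0.85, 1.00 and 1.29. A change of 0.5 baseline SD would then be reported as 0.42, 0.50 or 0.65.

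**Missing interval.** With 30 pairs, an observed change of 0.50 SD of change has a 95% confidence interval of about 0.12 to 0.88 (noncentral t). By the approximate formula above, these limits correspond to about 1165 and 21 per arm. A bare point estimate is weak for planning even without the attribution problem.

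**The case against.** The study is openly a small single-group pilot. Its primary outcome is enrollment, its size rests on feasibility, and Section 6.3 disclaims hypothesis testing and speaks of changes in mean scores. It also collects more direct evidence on the list: acceptability items ask whether the checklist made talking easier or got more questions answered (Section 4.2), and Section 12 compares recorded questions with those selected on the list. All this is true, and the primary outcome is untouched. But disclaiming tests does not settle attribution, the next sentence of Section 6.3 creates the planning use, and the acceptability and audiotape data are not a comparison with visits without the list.

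Two stronger readings are tempting and should not be adopted.

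- *A future trial would be under-sized.* This needs a positive non-list change and a controlled trial that takes the raw change as its between-arm difference. The documents state neither. The bias could also run the other way: scores may decline over the month, and Section 4.1 allows baseline surveys to be finished after a visit or by phone that week. If that is the prompt-list visit, part of the baseline would already be post-exposure.
- *Regression to the mean inflates the change.* The symptom screen opens with "Think about the last six months and the days you felt the worst", but it selects on symptoms, while the outcomes are self-care, confidence, communication and perceived efficacy. Nobody enters because of a low score on those scales.

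The companion's presence is also a weak rival explanation. Recruitment favors patients whose companion already comes into the exam room at most or all visits, so for many dyads it is usual practice.

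**Conclusion.** The point holds as a problem of attribution and of planning use. The stated objective cannot be met by this design, because the list is inseparable from the visit, its recording and the study contacts. The effect sizes in Section 6.3 are undefined in their denominator, carry no interval, and could mis-size a later trial in either direction if used as a between-arm difference. In the illustration, a trial of 64 per arm planned on d = 0.5 has 39% or 29% power if the list's true effect is 0.3 or 0.25, and 94% if it is 0.625. These figures rest wholly on assumed effects and shares, since the documents give none, and on a use of the estimate that the documents do not spell out. Feasibility and acceptability conclusions are unaffected. The plan should be changed, but the pilot's conduct need not be.

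**What to change.** - Synopsis and Sections 1 and 2: replace the reference to effects of the list with pre-post change after a prompt-list visit in the named outcomes.
- Section 6.3: state that the change is not attributed to the list, because it cannot be separated from the visit and study procedures, and that it will not be the assumed between-arm effect in a future trial.
- Section 6.3: define the denominator of the effect size.
- Section 6.3: for each behavioral outcome, report the mean change with a 95% confidence interval, the baseline and 1-month SDs, the SD of change, the pre-post correlation and retention. These are the quantities that help in designing a later trial.
- Base a future trial's target on a prespecified worthwhile difference.

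The cost is wording and a few summaries of data already being collected; means and SDs are already planned in Section 6.3, and Section 10 notes that the database can track attrition. No visit, participant or instrument is added. The downside is a more modest stated claim.

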3.1 Study Design

This is a single-group pre-post prospective study design.

3.2 Allocation to Treatment Groups and Blinding (if applicable) N/A

3.3 Study Duration, Enrollment and Number of Subjects. After IRB approval, the study will be active until 1-month follow-up data has been collected on all study participants (i.e., up to 30 dyads.) We anticipate that be no longer than 1 year.

3.4 Study Population. We will enroll HF patients, family members, and HCPs

Patient Eligibility

Ambulatory adult patients \geq 30 years old
Receive care in the UNC Cardiology or General Internal Medicine practice
Have a clinical diagnosis of HF
Currently prescribe a loop diuretic
Have a New York Heart Association class II-IV
Must speak English
Must have a working telephone or live with the patient

Family Member/Companion Eligibility

Must be at least 18 years old and able to give informed consent
Must be willing to participate in the intervention activities and provide informed consent
Must speak English
Must have a working telephone or live with the patient

Health Care Provider Eligibility

Must be an MD or advance practice provider (NP or PA) in the UNC cardiology or General Internal Medicine practice
Must be willing to have an enrolled patient visit audio-taped

4 STUDY PROCEDURES

4. 1 Screening/Baseline Visit procedures: Thirty HF dyads will receive the prompt list. Each dyad member will receive a prompt list to complete in the clinic waiting room immediately before their appointment. HF dyads will complete the prompt list without staff help. Completing the prompt list involves two steps. In step 1, participants will independently select from a list of questions or write in their own questions they would like to ask their health care provider during the visit. Patients will also be asked to select among a pre-determined list of behaviors they would like their family member to engage in during the visit (e.g., write down the providers instructions). In step 2, dyad members will collaboratively decide which questions to discuss during the visit. Participants will be encouraged to take the prompt list into the exam room and use it to facilitate communication with the HCP. The RA may take a picture of the prompt lists (which will not contain any identifying information, only a study id) to assess areas of agreement and disagreement between the dyad on what to discuss with the HCP. This information will inform future studies.

Potential participants will be identified using several sources: the Carolina Data Warehouse (CDW-H); the HF social support and family studies registry (SSR; IRB #11-0562); medical record audits by the study PI; and suggestions from HCPs.

After initial identification, we will query HCPs of potentially eligible patients to confirm the diagnosis of HF. (based on their clinical assessment), determine if the patients are appropriate to approach for possible study participation (procedures we have successfully used in our prior studies). When we provide participating providers with a list of their potentially eligible patients, we will all ask them to check how often the patient has a companion enter the exam room with them (none of the time, rarely, some visits, most visits, every visit). Patients will be considered "likely to be accompanied" if the provider indicates that a companion enters the exam room "most visits or every visit." We anticipate that the providers will be very accurate in predicting patients who usually bring a family member into the exam room, since these will be their regular patients. This method will be used to facilitate more efficient recruitment of patients most likely to be eligible for the study. For patients deemed ineligible by providers, we will ask providers to provide reasons why the patients should not be contacted, Provider approved patients will be approached by a research assistant (RA) to assess eligibility and possible interest in the study either during a scheduled clinic visit, via a provider-approved letter, or via telephone using an IRB approved telephone script. For those presenting for a clinic visit, the RA/SC will approach them about participation in the study. If they are interested, the study staff will consent the patient at that time and administer the baseline survey. If there isn't time to complete the entire baseline survey before the visit, we will finish the remainder of the survey either after the visit or via phone within the week of the visit.

We will use several approaches to identify and enroll family members: 1) If a family member has accompanied the patient to the clinic visit, the family member will be approached by a study coordinator at that time about participation in the study and they can provide written consent at that time, if they are interested and eligible. They will also be administered the baseline survey either before (or after the visit depending on the time) or via phone in the week of the visit. 2) If a family member is not present with the patient at a clinic visit, an IRB-approved study recruitment letter and a copy of the consent form will be sent home with the patient to give to a family member who may be interested in participating, and the family member can contact a study coordinator to discuss the study and/or mail in the signed consent form. The study team will provide a pre-paid self-addressed envelope to return the signed consent form. After receiving signed consent form, the study team will call the potential participants to schedule the baseline study interview for both members of the dyad. For potential participants identified through the CDW or from the HF social support and family studies registry, the study team will mail an IRB approved recruitment letter to potential patient participants. The letter will notify the patient that a family member (preferably who one attends medical visits with them) is required to also participate in the intervention, so they should discuss the study with family members and get their permission to share their contact (phone number or address) with the study team. The letter will include an opt-out form that potential participants may return using pre-paid, self-addressed envelope that will accompany the recruitment letter. We will follow-up with potential patient participants via telephone 1 week after the letters have been mailed. If they are interested in participating and have identified a family member who is interested, the study team will obtain verbal consent from each person and a written consent form will also be mailed to them to sign and return to the study team. The RA/Project Coordinator will also schedule the baseline study interview. If the patient and family member provide verbal consent, but do not return the written consent form via mail, we will have them sign a written consent form at the time of baseline study interview. We will make it clear to the patient and family member that both individuals must be eligible and provide informed consent for either to be eligible to participate in the study. An RA/Study coordinator will obtain informed written consent for all eligible and interested dyads.

Partners in Health Eligibility SCREENING FORM

The following form will be used to determine eligibility for Patients:

Partners in Health: Pilot test of a Pre-Visit Question Prompt List to Enhance Engagement of heart failure (HF) patients and Family Members During Medical Visits

Patient Eligibility Form

Research Assistant: _____

Study ID#: _____

QUESTIONS TO ASK PATIENT TO VERIFY ELIGIBILITY

DATE: _____

1. Is English your preferred language?"
YES NO
2. "Do you see a health care provider at the UNC Cardiology Clinic?"
YES NO
3. "Do you have a diagnosis of Heart Failure (or Diastolic Dysfunction)?"
YES NO
4. "Do you take a loop diuretic medication?" (e.g. Furosemide, Lasix, Bumetanide, Bumex, Demadex, Torsemide)
YES NO
5. "Do you take a thiazide diuretic medication?" (e.g. Hydrochlorothiazide, HydroDIURIL, Chlorothiazide, Diuril, Chlorthalidone, Metolazone, Zaroxolyn, Indapamide, Lozol)
YES NO
6. "What is your current age?"
7. "Do you require assistance with basic activities of daily living?"
YES NO
8. "Do you live in a nursing home or care facility?"
YES NO

(Patients who receive nursing home services (including help with basic activities of daily living are NOT eligible to participate; patients living independently in senior centers or independent living facilities ARE eligible)

9. Do you have a working telephone?
YES NO
10. Do you agree to have one of your visits with your provider audiotaped
YES NO
11. Symptom Assessment (Patient must answer "YES" to at least one question)

"Think about the last six months and the days you felt the worst.

So, on your worst days..."

1) "How many city blocks could you walk before getting short of breath?"

If states a specific number, has symptoms (Number _____ = symptoms)

YES

If says can walk as far as s/he wants—go to #2

NO

If unable to walk enough to answer question, go to 1a below

Unable to answer

2) "Did you have to walk at a slower pace than normal to keep from getting short of breath?"

If says Yes, has symptoms

YES

If says No—go to #3

NO

3) "If you had to rush or hurry, did you get short of breath?"		
If says Yes, has symptoms		YES
If says No—go to #4		NO
4) "How many flights of stairs could you climb without getting short of breath or needing to stop to catch your breath?"		
If less than 2 flights or needs to stop at 2 flights catch breath, has symptoms		YES
If can walk up 2 or more flights then is truly class I and does not have symptoms		NO
(If unable to answer question 1 above, ask the following questions)		
1a) "Have you experienced swelling of the legs or ankles due to excess fluid?"	YES	NO
1b) "Do you sleep on more than one pillow at night to help you breathe easier?"	YES	NO

TO BE COMPLETED BY RESEARCH ASSISTANT ELIGIBILITY CRITERIA—for Heart Failure Patients

Patients must have ALL of the following eligibility criteria.

1. Relationship – Patient must be seen by a health care provider at the UNC Cardiology clinic at least one time before? YES
2. Diagnosis – Carry a clinical diagnosis of Heart Failure or Diastolic Dysfunction YES
3. Medications– Currently prescribed a loop or Thiazide diuretic. YES

Loop Diuretics: Bumetanide (Bumex®), Torsemide (Demadex®), Furosemide (Lasix®)

Thiazide Diuretics: Hydrochlorothiazide (HydroDIURIL®), Chlorothiazide (Diuril®), Chlorthalidone, Metolazone (Zaroxolyn®), Indapamide (Lozol®)

4. Symptoms – Have New Class II, III or IV symptoms now or in the past 6 months YES
5. Age – Over the age of 21 YES
6. Communication – Speak English and have adequate hearing to communicate and talk in person or on the phone. YES
7. Audiotaping – Must agree to have a visit audiotaped YES

INELIGIBILITY CRITERIA

Patients will be ineligible if they meet ONE of the following criteria:

1. Do not speak English
2. Have significant cognitive impairment (e.g. a diagnosis of dementia/severe cognitive impairment)
3. Have significant psychiatric impairment (e.g. schizophrenia)

4. Require assistance with Activities of Daily Living (ADL)
5. Live in a nursing home

IS THE PATIENT ELIGIBLE? (Circle one) ELIGIBLE INELIGIBLE

Partners In Health Eligibility SCREENING FORM

The following form will be used to determine eligibility for Family Members:

Research Assistant: _____

Study ID#: _____

QUESTIONS TO ASK INDIVIDUAL TO VERIFY ELIGIBILITY

1. "What is your current age?" _____
Family member must be at least 18 years old.

2. "What is the highest grade you completed?" _____
(If 6th grade or below, or if have knowledge that family member is illiterate, have witness present when signing consent)

3. Do you have a working telephone or live with the patient?
YES NO

4. "Is English your preferred language?"
YES NO

If family member does not speak English, then they are ineligible to participate.

The family member and the patient MUST answer YES to the following question for the visit companion to be eligible to participate.

Read the following definition to the participant:

"Family is broadly defined as two or more persons who are related in any – biologically, legally, or emotionally. Therefore, "family" is defined by the patient.

5. Do you think the patient considers you family?

YES NO

If "yes", confirm with the patient. If the patient does not agree then the individual is not eligible to participate.

IS THE INDIVIDUAL ELIGIBLE AS A FAMILY MEMBER? (Circle one)

ELIGIBLE INELIGIBLE

BASELINE ADMINISTRATION PROTOCOL

The following is protocol for the administration of the **BASELINE QUESTIONNAIRES** to study participants.

The baseline questionnaires can be collected in 3 different ways: 1) on the phone with the participant after the participant has provided verbal consent; 2) in person, after the participant has completed their informed consent; or 3) by phone after the participant has met with the RA/SC in person at a medical appointment at enrollment and completed their informed consent but did not have time to complete the baseline questionnaires.

After participants have consented (verbally or by in-person informed consent), the **BASELINE QUESTIONNAIRES** will be administered.

The RA/SC will need the following:

- iPad and power source for data collection into REDCap
- Paper copies of the questionnaire
- Answer key for the patient
- Pen/pencil for both the RA/SC and the subjects

Note: For iPad administration of the surveys, refer to the REDCap section in this protocol.

After the participant has provided consent, the RA/SC will administer the baseline questionnaires. It is important to speak clearly and slowly so that the participant can understand what is being asked, especially if the baseline data collection occurs over the phone.

Baseline data collection is preceded by the following prompt:

Hello, _____. This is [NAME] calling from UNC Health Care. I'm calling about the Heart Failure Study that you joined last week.

As a first step in the study, I'd like to ask you a few questions about your health and your healthcare experiences. Our conversation should take about 15 minutes. Is this a good time to talk?

[IF YES, PROCEED]

[IF NO, RESCHEDULE FOR A LATER DATE/TIME]

You are in this study because you have heart failure. Doctors sometimes call this congestive heart failure, an enlarged heart, or fluid in the lungs.

During our conversation, I'll ask you questions about yourself, your visit companion, and your interactions with your doctor. Your "visit companion" is the family member or friend who comes with you to your health appointments. Your "doctor" is the doctor, nurse practitioner, or other health care provider who you usually see during your visit.

After completing the prompt and if the participant is able to conduct their data collection at that time, the RA/SC will collect their data either by using one of the following: 1) paper data collection materials; 2) the iPad REDCap application; or 3) by computer using the REDCap online data capture system. Regardless of the way in which the data is collected, each data collection will be administered uniformly to all participants.

Below are the **BASELINE QUESTIONNAIRES** with their respective variables for analysis for patients

List of measures included in this questionnaire:

1. Relationship with companion
2. Companion involvement
3. Closeness with companion
4. Health literacy
5. Knowledge of heart failure+
6. Self-care behaviors
7. Self-efficacy related to self-care
8. Perceived health status
9. Heart failure symptom severity
10. Communication with provider
11. Perceived efficacy in interactions with doctor
12. Perceived social support
13. Demographic/background questions

*Note that the Baseline Questionnaires **for companions** includes the following measures, which parallel the patient questionnaires:

List of measures included in this questionnaire:

1. Relationship with patient
2. Companion involvement
3. Closeness with patient
4. Knowledge of heart failure
5. Caregiver care behaviors
6. Self-efficacy related to patient care
7. Perceived efficacy in interactions with doctor
8. Demographics
9. Health literacy

Companion for visit with doctor

1. **Will you have a companion, such as a family member or friend, come with you to visit your doctor during this study? Variable name: accompanied**

- a. Yes
- b. No

IF NO:

- 2. Does someone usually go with you to your medical appointments? **Variable name: usual_accomp**
 - a. Yes
 - b. No

Relationship with Companion

[IF PARTICIPANT WILL NOT HAVE A COMPANION COME WITH THEM TO THEIR APPT, ASK ABOUT THE PERSON WHO USUALLY GOES WITH THEM. IF PARTICIPANT DOES NOT USUALLY HAVE A COMPANION COME WITH THEM TO THEIR APPT, SKIP AHEAD TO HEALTH LITERACY.]

